Side effects that are associated with the treatment such as local inflammation due to an inadequately placed or polished restoration, and/or oral lichenoid reactions that are in direct vicinity to the study restoration, will be documented in detail and the patient affected will be excluded from the study. In this case, the restoration will be replaced by another material as soon as possible. In addition, a restoration that fractures due to a mechanical failure of the material will also be replaced as soon as possible. It is possible to have an irreversible pulpitis develop after placement of the restoration, as often times happens during routine dental treatment. In this case, the subject will be excluded from the study and will have to continue with the appropriate treatment at the dental office of their choice at their own expense.

Biostatistical analysis

Study design

The goal of this clinical trial is to show that Venus Pearl (a development based on the material "Venus Diamond", Heraeus Kulzer, Hanau – Germany) has a better score than the commercially available control material (Filtek Supreme XTE, 3M/ESPE, Seefeld – Germany and Filtek Supreme Ultra, 3M/ESPE, USA) for the restoration of class II-cavities. Patients older than 18 who show an interproximal (Class II) carious lesion or an existing defective restoration requiring therapy on premolars or molars will be included.

For the determination of the superior outcomes of both fillings a pre-specified evaluation scheme will be used.

The assessment of the replacement will be performed at four time points (1 week, 6 months, 12 months and 24 months after replacement). For the primary analysis the score will be considered 24 months after the replacement.

The primary endpoint will be a mean score calculated as following: There are three aspects to be assessed: aesthetic, functional attribute and biological parameters. For each aspect there are respectively four categories where each has to be assessed on a scale from 1 to 5. Thereby 1 means clinically excellent, 2 means clinically good and 3 means clinically disappointing. This assessment form is given in FDI World Dental Federation (J Adhes dent 9 (1), 121 – 147 (2007)). For each

patient the points of the 12 different evaluation criteria (four categories in the three parts) will be summed up resulting in a score that ranges from 12 to 60.

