Secondary endpoints are the evaluation of secondary caries, plaque accumulation and gingival reactions and the comparison of the primary score at week 1, month 6, month 12 and month 24 after restoration. Beside this, the single components of the three categories of the primary endpoints will be compared.

Randomization, stratification and blinding

This is an observer-blind clinical trial, e.g. evaluators will not know the given treatment. Restorations will be distributed evenly between the control and the experimental groups using randomization lists.

The application of the two restorative materials is limited to premolars and molars and to achieve a uniform distribution of both tooth types, stratification with the strata premolar and molar will be performed in the randomization process. In addition randomization will be stratified by center.

Randomization will be performed centrally by the Institute of Biometrics to ensure admission before allocation. The randomization will not be based on patients' names, rather than on a scheduled visit, to avoid problems with patients that do not show up for the treatment.

In order to guarantee an objective evaluation at the different time points, the Case Report Form has separate sections for each evaluation, so that the evaluators only use the form for the present examination. Through this method, the evaluator cannot see which assessment he/she gave during previous examinations. These sections will only have the patient number information.

The treatment allocation and the corresponding patient ID will be kept in a separate file that is inaccessible for operators and evaluators.

Description of the primary analysis and key secondary analysis

In the primary analysis the superiority of Venus Pearl will be investigated. Therefore the primary analysis will be conducted on the ITT population, e.g. in all randomized patients. The missing values will be replaced as described below. For the comparison of the scores of the Venus Pearl and Filtek Supreme group an ANOVA will be performed 24 months after restoration. Here, center, tooth type and treatment will be incorporated as covariables. The study is successful if the 95 % confidence interval for the treatment effect (Venus Pearl – Filtek Supreme) is below 0.

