In the secondary analysis, caries (yes/no), plaque accumulation (yes/no) and BOP/ Pocket depths, will be examined with logistic regression models including center and tooth type as independent variables. Sensitivity analysis will be applied using mixed models.

If the study is extended to 4 years, the additional appointments taking place 3 and 4 years after restoration placement (late follow-up) will be evaluated descriptively using the same line as described above for the primary analysis.

Missing values

Missing values may be recorded when patients miss examination appointments. In this case the missing values will be replaced by the "last observation carried forward", where the assessment of the previous examination will be carried over to replace the missing value.

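### No rule says how a failed, replaced or excluded restoration enters the 24-month primary score, so the score can omit loss and fracture

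*Combined protocol and SAP*

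**What the plan says.** - **Objective of the study** puts loss and fracture of the restoration first among the primary endpoints.
- **Assessment of restorations** schedules scoring at 1 week and at 6, 12 and 24 months. It describes no scored visit at the time of a failure.
- The same section then covers adverse outcomes. For side effects, such as "local inflammation due to an inadequately placed or polished restoration" or a lichenoid reaction next to the filling, these "will be documented in detail and the patient affected will be excluded from the study", and another material is placed. For fracture, "a restoration that fractures due to a mechanical failure of the material will also be replaced as soon as possible"; whether the patient stays in follow-up is not stated. For irreversible pulpitis, "In this case, the subject will be excluded from the study and will have to continue with the appropriate treatment" outside the study. Loss is not mentioned here.
- **Biostatistical analysis, Study design** defines the primary score as 12 items graded 1 to 5 and summed, range 12 to 60, with lower scores better. "For the primary analysis the score will be considered 24 months after the replacement". In that sentence the word replacement means the study restoration itself.
- **Description of the primary analysis** says "the primary analysis will be conducted on the ITT population, e.g. in all randomized patients" and "The missing values will be replaced as described below". Success means that the 95% confidence interval for test minus control lies below 0. A mixed-model sensitivity analysis is named without detail.
- **Missing values** opens with "Missing values may be recorded when patients miss examination appointments" and gives LOCF as the remedy for that case. It is the only imputation rule in the document.

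**The concern.** The plan keeps everyone in the primary analysis, removes or refills some restorations before 24 months, and gives those restorations no score. Two outcomes are then possible, and both can leave the failure out.

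If the patient has left, the 24-month value is missing and LOCF is the only rule available. A restoration graded well at 12 months whose patient is excluded at 15 months may then enter at its 12-month score. If a fracture has been refilled and the patient stays, nothing is missing, LOCF is not triggered, and the new filling may be graded in place of the failed one. The wording does not rule this out, because the plan also calls the study restoration a replacement.

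The single confirmatory test could therefore miss the events that the objective lists first. No separate comparison of failures by arm is planned that would show what the score hides, and the planned component comparisons use the same scores. If the rule is left open, it may be chosen after the results are known.

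**Working it through.** **Text check.** Every section was searched for a score given to a lost, fractured, replaced or excluded restoration, for a scoring visit at failure, and for a statement on whether new material is scored. None was found.

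**Inputs from the documents.** 90 restorations per arm (45 × 2 sites); score range 12 × 1 = 12 to 12 × 5 = 60; success if the 95% CI lies below 0. The documents give no SD, effect size, power or failure rate, so there is no planned figure to reproduce.

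**Ceiling from the documents.** One hidden failure can remove at most (60 − 12)/90 = 48/90 = 0.53 points from an arm mean.

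**Assumed inputs (illustration only).** A failure moves one item from 1 to 5 (4 points, or 4/90 = 0.04 of an arm mean) or three items (12 points, 12/90 = 0.13). SD is 2 or 3, and control mean 16 when intact. Restorations are treated as independent. Centre, tooth type and clustering within patient are not modelled.

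**Formula.** With cost c per failure, failure rates pT and pC, and all failures hidden:

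observed difference = true difference − c × (pT − pC).

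With a true difference of 0, the trial shows:
- 6% vs 1%: −4 × 0.05 = −0.20 (one item); −12 × 0.05 = −0.60 (three items).
- 3% vs 2%: −4 × 0.01 = −0.04; −12 × 0.01 = −0.12.

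The standard error is SD × √(2/90) = 0.298 (SD 2) or 0.447 (SD 3). The noncentral t distribution with 178 degrees of freedom gives the all-hidden column. The other columns come from simulation with 40,000 runs per cell. Entries are the chance of declaring superiority, SD 2 / SD 3, against a nominal 2.5%.

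| Failures, test vs control | Items per failure | All hidden | Half hidden | None hidden |
|---|---|---|---|---|
| 3% vs 2% | one | 3.4% / 3.1% | about 3% / 3% | 2.5% to 3% |
| 3% vs 2% | three | 5.9% / 4.5% | about 4% / 3% | 2.5% to 3% |
| 6% vs 1% | one | 9.8% / 6.5% | 5% / 4% | about 2.5% / 2.5% |
| 6% vs 1% | three | 51.7% / 26.6% | 14% / 9% | 3.5% / 3.0% |

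**When the test material really is 1 point better if intact.** At 6% vs 1%, counting every failure gives −1 + 4 × 0.05 = −0.80 (one item) or −1 + 12 × 0.05 = −0.40 (three items). Hiding them all gives −1.0. The advantage is overstated but real. Reversing it needs more than 1/0.05 = 20 points, or five items, per failure. At 3% vs 2% it would need 1/0.01 = 100 points, above the maximum of 48, so it cannot happen.

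**Opposite direction.** At 1% vs 6%, one item per failure and the same 1-point advantage, superiority is declared in 92%/60% with all failures hidden and about 96%/74% with all counted. Hiding failures can therefore also work against the test material.

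**The case against.** The strongest reply is that the plan does not instruct anyone to carry a pre-failure score forward. LOCF is tied to missed appointments, so an excluded or refilled restoration may fall outside it. That is correct. A reader might infer that LOCF definitely applies, but the text supports only that it is the likely default, because missing values in the primary analysis are to be replaced and no other rule is given. The alternative reading leaves the case undefined, which is also a defect in a primary analysis.

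Second, masking is partial. A failure still in place at a scheduled visit is graded, and that grade is carried forward. This stands, and it is why the all-hidden column is an upper case.

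Third, the population conflict is weaker than it looks. Exclusion can be read as the end of follow-up, since the analysis keeps all randomised patients. This also stands, but it supplies no score.

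Fourth, the word bias assumes that failures are meant to count in the score. The score definition does not say so; the endpoint list in the objective supports it.

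Finally, one might take the 52% as the expected error rate. It needs a sixfold imbalance in failures, three items per failure, SD 2 and every failure hidden. Nothing in the documents supports that combination.

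**Conclusion.** The gap is in the text and needs no assumed figure: the plan has no rule for the 24-month score of a failed, replaced or excluded restoration, and its nearest rule can leave loss and fracture out of the primary comparison. It must be closed before the data are analysed.

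The size and direction of the effect are unknown. The documents give only the ceiling of 0.53 points of an arm mean per hidden failure. The comparison favours the arm with more hidden failures and is unaffected if they are equal in number and cost. On the stated assumptions the false-success rate is close to nominal at 3% vs 2% failures (about 3% to 6%) and clearly raised only with a large imbalance. The documents do not support a conclusion that the trial will falsely declare superiority, or that the gap favours the test material.

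**What to change.** State in the SAP:

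1. For a restoration lost, fractured or replaced for material failure, the pre-failure total is not carried forward, and replacement material is never scored in the primary analysis.
2. The blinded evaluator scores the failed restoration on the FDI form at the failure visit where one occurs, without delaying or changing care. Where none occurs, the blinded evaluator scores it from the documented event and photographs. That score is carried to 24 months.
3. Items the failure directly affects, including those that cannot be assessed because the restoration is lost, take the worst grade of 5. Unaffected items keep their last value. Setting all 12 items to 5 is a sensitivity analysis. Linking grade 5 to failure is a choice made here; the plan gives 5 only as the end of the scale.
4. Exclusions for pulpitis or for inflammation related to placement or polishing are reported separately by arm, because counting them against the material is debatable. A sensitivity analysis counts them as failures. The SAP should name the value they take in the primary analysis and say in advance which group lichenoid reactions belong to.
5. Failures are reported by arm and type as a difference with a 95% CI. This is an estimate and not a test to rely on: Fisher exact power is 26% at 6% vs 1%.

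The patient-level exclusion in Assessment of restorations must be reconciled with the all-randomised analysis. Recruitment of patients allows up to four restorations per patient, so data on the patient's other study restorations should be kept.

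The cost is SAP wording, one unscheduled CRF page and added variance. On the assumed inputs with a 1-point advantage and 3% failures in each arm, power (SD 2 / SD 3) falls from 92%/60% to 88%/58% at one item per failure and 65%/45% at three. With every failure set to 60 it falls to about 15%/15%, which is why that version is only a sensitivity analysis.

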**Clinical investigation of a new nanohybrid resin composite Venus Pearl in class 2
cavities– a multi-center study**

NCT01925040

Study Protocol and Statistical Analysis Plan

Date 15.08.2013

Objective of the study

The objective of this study is to compare the performance of the composite resin Venus Pearl (a development based on the material "Venus Diamond", Heraeus Kulzer, Hanau-Germany) and the commercially available control material Filtek Supreme XTE (3M/ESPE, Seefeld-Germany- available for the study center in Germany) and its equivalent material Filtek Supreme Ultra (3M/ESPE, Seefeld-Germany- available for the study center in the United States) for the restoration of class II-cavities. Primary endpoints of the study are: loss of the restoration, fracture of the restoration, postoperative sensitivity, marginal discoloration and marginal gap or step formation. Secondary endpoints are the evaluation of secondary caries, plaque accumulation and gingival reactions.

Ethics

The study is in accordance with the declaration of Helsinki. The study protocol will be assessed and approved by the ethical committee of Hannover Medical School as well as by the Institutional Review Board of the Oregon Health and Science University (OHSU). Each patient will receive a detailed information leaflet and has to declare in writing her or his consent to participate in the study. This written informed consent can be cancelled by the patient at any time without justification.

Study design

The study will be executed as a multi-center, single-blinded and randomized clinical investigation.

Multicenter, single-blinded, and randomized clinical investigation. Study sites are the Department of conservative Dentistry, periodontology and Preventive Dentistry at the Hannover Medical School, Hannover, Germany, and the Department of Restorative Dentistry at the Oregon Health and Science University, Portland, Oregon, USA. Coordination of the study at both study sites is done by the Hannover Medical School.

General information

Time frame of the study: 2 years (with optional extension to 4 years)

Number of patients/ restorations: 90 comparable cavities per Institution (180 total), randomization

Test material: n=90 (n = 45 per site)

Control material: n=90 (n = 45 per site)

Recruitment of patients

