Patients will be recruited by the Department of Conservative Dentistry, Periodontology and Preventive Dentistry of the Hannover Medical School and the Department of Restorative Dentistry of the Oregon Health and Science University (OHSU). Patients who require a class II restoration will be included in the study (see inclusion criteria). Each patient will be eligible to receive up to four restorations, with either a test or a control material. Patients will be given detailed information regarding the study before they are included in the study. Patients will receive an information leaflet and a copy of their signed informed consent form. Patients, who could not follow their examination appointments, will be contacted by phone to arrange a new appointment. Patients who miss three appointments will be classified as "drop-outs", which means that no further appointments will be scheduled for these patients regarding this study.

Inclusion criteria

- Patients should be 18 years and older.
- Study teeth should have an interproximal (Class II) carious lesion or an existing defective class II restoration requiring restorative therapy on premolars or molars.
- The maximum cavity depth determined by the radiograph will be D2 (Tyas classification).
- The teeth included in the study need to have a proximal contact with the adjacent tooth and be in occlusion with the opposing dentition.
- The teeth included in the study should be vital with no signs of pulpal pathology.
- Patients that report brushing regularly without severe gingival inflammation and/or extensive caries.
- Patients should have no allergies or systemic diseases which inhibit the treatment.
- Patients should have voluntary participation and sign a written informed consent form.
- Patients should be willing to participate in the recall/re-examination appointments.

Exclusion criteria

- Simultaneous participation in another study about dental restorative materials.
- Written informed consent form not signed.
- Nonvital pulp / periapical lesion.
- Insufficient oral hygiene despite detailed instructions.
- Pregnancy/ breast feeding before placement of the study restoration.
- Minors.
- Severe malocclusion/ malalignment/ traumatic occlusion/ bruxism.
- Known allergy to any components present in any of the materials that are used for this study.
- Unclear mucosal alterations, e.g. oral lichenoid reactions/lesions.

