- Severe medical complications (organ transplants, cancer, immune-compromised, long-term antibiotic or steroid therapy).
- Infectious diseases such as HIV/Aids, Hepatitis, etc.
- Application of bleaching products less than 14 days before placement of the restoration.
- Orthodontic treatment during the study.
- Xerostomia.
- Untreated periodontal diseases.
- Rampant or extensive caries present.
- Systemic diseases with potential oral manifestation.
- Sufficient isolation according to the criteria of adhesive techniques not possible, e.g. application of rubber dam.
- Direct adhesive restoration not indicated.
- Replacement of more than one cusp indicated.
- Dental fears patients.
- Cracked tooth syndrome in study tooth.

Assessment of restorations

Restorations will be assessed by the evaluator per site at baseline (1 week after placement), as well as after 6, 12 and 24 months. Evaluations will be documented within the source data (patient's documentation) and in the Case Report Form (CRF).

Photographs of the teeth will be taken after the cavity preparation and after the restoration has been placed and finished as well as at each evaluation appointment.

If the study will be extended to 4 years, two additional assessments will be done, after 3 and 4 years (36 and 48 months) and patients will be informed of a possible request for recall at years 3 and 4 at the initiation of the study.

The evaluations will be based on the Recommendations for Conducting Controlled Clinical Studies of Dental Restorative Materials, Science Committee Project 2/98 - FDI World Dental Federation (J Adhes Dent 9 (1), 121-147 (2007)).

Partial impressions of the study teeth will be taken at baseline and during all subsequent examinations of the restorations with an addition-type silicone material (Flexitime Putty and Correct Flow, Heraeus, Hanau-Germany) and a plastic inlay tray. These impressions will be used to determine the in-vivo wear of the restorations by means of replica using a resin material (DuroCit, Struers, Willich-Germany) by means of scanning electron microscopic-warden images.

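### A side effect or pulpitis at one restoration excludes the whole patient, so up to three unaffected study restorations can lose their remaining examinations, including the primary one at 24 months

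*Combined protocol and SAP*

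**What the plan says.** Three parts of the document meet here.

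**Unit of the trial.** General information plans "90 comparable cavities per Institution (180 total), randomization", with 45 restorations per material and site. Recruitment of patients states: "Each patient will be eligible to receive up to four restorations, with either a test or a control material". Under Randomization, stratification and blinding, "Restorations will be distributed evenly between the control and the experimental groups using randomization lists". The same section adds: "The randomization will not be based on patients' names, rather than on a scheduled visit". The document does not settle whether one patient can hold both materials.

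**Unit of exclusion.** The last paragraph of Assessment of restorations covers three kinds of event:
- Treatment-associated side effects (the examples are local inflammation and oral lichenoid reactions next to the study restoration) "will be documented in detail and the patient affected will be excluded from the study".
- Irreversible pulpitis: "In this case, the subject will be excluded from the study and will have to continue with the appropriate treatment".
- Mechanical fracture: "a restoration that fractures due to a mechanical failure of the material will also be replaced as soon as possible". No exclusion of the patient is stated.

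**Examinations and analysis.** "Restorations will be assessed by the evaluator per site at baseline (1 week after placement), as well as after 6, 12 and 24 months". The primary score is the one at 24 months. The primary analysis is ITT, which the plan explains as every randomized patient. Missing values describes last observation carried forward (LOCF) for missed appointments and does not mention excluded patients.

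**The concern.** The trial allocates and counts restorations, but after two kinds of event it withdraws people. A site that follows the text literally stops recalling the patient. The patient's other study restorations then go unexamined, although nothing has happened to them and they could still be scored.

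Three things are at stake:
- Primary data that could be observed at 24 months are not collected, in a trial whose primary analysis is ITT.
- The analysis of these restorations is undefined. The LOCF rule does not name exclusion. If it is applied anyway, the score carried forward may be as old as the 1-week examination.
- After a lichenoid reaction at one restoration, study observation also ends for other study restorations in the same mouth, which may be of the same material.

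How the affected restoration itself should be scored is a separate question.

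**Working it through.** **1. The plan's own figure.** 2 sites × 2 materials × 45 = 180 restorations, as stated. The document gives no effect size, standard deviation, power or dropout rate, so there is no sample-size calculation to reproduce.

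**2. Unaffected restorations per event.** The maximum is four per patient, so one event can take at most 4 − 1 = 3 others with it. If every patient had four restorations, 180 / 4 = 45 patients would be enrolled; if every patient had one, 180 patients.

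**3. Which score remains.** If LOCF is extended to excluded patients, an unaffected restoration would enter the 24-month analysis with:
- its 1-week score, if the exclusion comes before month 6;
- its 6-month score, if between months 6 and 12;
- its 12-month score, if between months 12 and 24.

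If LOCF is not extended, the plan gives no value. An event first found at the 24-month visit need not cost any other restoration its primary examination.

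**4. Whether the other arm is touched.** If restorations within a patient are allocated independently 1:1, the chance that at least one of the other k − 1 restorations has the other material is 1 − 0.5^(k−1): 50% for k = 2, 75% for k = 3 and 87.5% for k = 4. If all of a patient's restorations receive the same material, it is 0%.

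**5. Expected number losing follow-up.** Two inputs are assumptions, because the document gives neither: p, the risk per restoration of an excluding event before the 24-month examination, and k, the number of restorations per patient (taken as equal for all patients). Events are assumed independent.
- Only the affected restoration stops: 180 × p.
- The whole patient is excluded: 180 × [1 − (1 − p)^k].

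| p | Affected only | Patient excluded, k = 2 | Patient excluded, k = 4 |
|---|---|---|---|
| 1% | 1.8 | 3.6 | 7.1 |
| 3% | 5.4 | 10.6 | 20.6 |
| 5% | 9.0 | 17.6 | 33.4 |

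For example, with p = 3% and k = 4: 1 − 0.97^4 = 0.1147, and 180 × 0.1147 = 20.6, against 180 × 0.03 = 5.4.

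Unaffected restorations lost are the difference: 3.6 − 1.8 = 1.8 (1% of 180) at p = 1% and k = 2, and 33.4 − 9.0 = 24.4 (about 14% of 180) at p = 5% and k = 4. At k = 1 the difference is zero. Positive correlation of events within a patient reduces it, because fewer of the restorations lost are unaffected ones.

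**The case against.** **The wording may be loose.** The unit is unclear elsewhere too: the primary score is summed per patient, ITT is explained by patients, and randomization is tied to a visit. Perhaps the sponsor meant that only the affected restoration leaves. But the same paragraph speaks of the restoration when it means one, and the pulpitis sentence sends the person to another dental office. A site can reasonably read it literally, so the text needs changing either way.

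**There may be a rationale.** Known allergy to the study materials and unclear mucosal alterations such as lichenoid lesions are patient-level exclusion criteria at entry, so removing a patient who develops such a reaction is consistent with them. Nor is it in itself a contradiction that a mechanical fracture is treated differently. Both points stand. They explain why a patient might leave, but they do not say what happens to the 24-month data of the other restorations.

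**The loss may be small.** This also stands. Four restorations in every patient is an extreme assumption when extensive caries is an exclusion criterion. At p = 1% and k = 2 the extra loss is 1% of the restorations.

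**A reader might infer that the rule favours one arm**, because the lost restorations sit in susceptible mouths and would have scored worse. The documents do not support this. One listed cause is a poorly placed or polished restoration, a fault at one tooth, and pulpitis is described as a common event in routine care. Only the lichenoid reaction readily suggests a susceptible patient. The argument also needs correlation within the mouth, whereas the figures above assume independence, so the largest loss and a selective loss should not be claimed together.

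**Conclusion.** The point holds as an avoidable loss of primary data and a conflict between the exclusion wording on one side and restoration-level allocation and the ITT population on the other. For an event before month 24, up to three unaffected restorations per patient lose their remaining examinations, including the primary one.

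The size cannot be determined from the documents. The illustrated range runs from no extra loss (k = 1), through 3.6 against 1.8 restorations (p = 1%, k = 2), to an extreme of 33.4 against 9.0 (p = 5%, k = 4). It rests on assumed p and k and on independent events.

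Three stronger readings should be avoided:
- That the loss biases the comparison in a known direction. Selective loss is possible, but its direction is unknown.
- That these restorations disappear from the analysis, or that LOCF certainly fills them. The plan says neither.
- That an event on one material necessarily deletes data from the other. This depends on whether one patient can hold both materials, which the plan leaves open.

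This is a cheap improvement worth making, with an effect that may be small.

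**What to change.** Reconcile the two exclusion sentences in Assessment of restorations with restoration-level allocation and the ITT population, by separating the end of follow-up for the affected restoration from the patient's participation in the study:
- The event is recorded for the affected restoration.
- The patient's other study restorations continue to be examined at whichever of the scheduled 6-, 12- and 24-month visits remain, unless the patient withdraws consent.
- Those restorations enter the primary analysis with their observed scores.

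This concerns data collection and analysis only. Clinical care of the patient and of the affected tooth stays as the protocol has it.

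**Cost.** A short amendment and matching consent wording, to be handled by both ethics bodies (Hannover and Oregon). The visits are already in the schedule and no new procedure is added. The downside is that patients who have had an event are asked to keep attending recalls.
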